10.8 Resistance Analyses

If possible, subjects treated with study drug during the Treatment Period who experience virologic failure will have resistance testing conducted if 1) they have on-treatment breakthrough; 2) if they have post-treatment relapse, with a study drug duration ≥ 77 days for subjects assigned to 12 weeks of treatment or with a study drug duration ≥ 154 days for subjects assigned to 24 weeks of treatment; or 3) if they have at least 6 weeks of treatment and fail to suppress by Week 6 (i.e., meet virologic stopping criteria). Subjects meeting one of these criteria will be referred to as subjects in the primary virologic failure (PVF) population, and a listing by subject that includes HCV subgenotype, IL28B genotype, reason for non-response, time point(s) sequenced as closest to time of VF, and HCV RNA value at the VF time point(s) will be produced for these subjects. In addition,

all listings described below will display HCV subgenotype and reason for non-response in the subject identifier for each subject. A separate listing will delineate all subjects in the PVF population for whom no sequencing was performed (e.g., lost to follow-up while HCV RNA \leq 1000 IU/mL).

Only samples with an HCV RNA level of \geq 1000 IU/mL will undergo sequence analysis in order to allow accurate assessment of products of amplification. Therefore if the HCV RNA level at the time of virologic failure (VF) is $<$ 1000 IU/mL, the sample closest in time after the failure with an HCV RNA level \geq 1000 IU/mL will be used if available. If deep sequencing is not performed, clonal sequencing of a given target will be performed only if no variants are detected at signature resistance-associated amino acid positions by population sequencing in that sample. In addition, clonal sequencing may be performed if there is a complex mixture of amino acids at one or more signature resistance-associated position.

The regions of interest for population or deep sequencing from all evaluated time points in this study are those encoding NS3 amino acids 1 – 181, NS5A amino acids 1 – 215, and NS5B amino acids 300 – 581. The prototypic reference sequences used for analysis will be H77 for genotype 1a or Con1 for genotype 1b.

For each DAA target, resistance-associated signature amino acid variants will be identified by AbbVie Clinical Virology. Amino acid positions where resistance associated variants have been identified in vitro and/or in vivo are 1) for ABT-450: 36, 43, 55, 56, 80, 155, 156, and 168 in NS3 for genotype 1a; 56, 155, 156, and 168 in NS3 for genotype 1b; 2) for ABT-267: 28, 30, 31, 32, 58, and 93 in NS5A for genotype 1a; 28, 29, 30, 31, 32, 58, and 93 in NS5A for genotype 1b; and 3) for ABT-333: 316, 414, 446, 448, 451, 553, 554, 555, 556, 558, 559, and 561 in NS5B for genotype 1a; 316, 368, 411, 414, 445, 448, 553, 556, 558, and 559 in NS5B for genotype 1b. The final list of amino acid positions where resistance-associated variants have been identified will be included in the CSR.

The following definitions will be used in the resistance analyses:

- Baseline variant: a variant (by population or deep sequencing) in a baseline sample determined by comparison of the amino acid sequence of the baseline sample to the appropriate prototypic reference amino acid sequence for a given DAA target (NS3, NS5A, or NS5B).
- Post-baseline variant by population or deep sequencing: an amino acid variant in a post baseline time point sample that was not detected at baseline in the subject and is detectable by population or deep sequencing.
- A post-baseline variant by clonal sequencing: a variant at a signature resistance-associated amino acid position that was not present in a subject by population sequencing at baseline that is detected in a post-baseline sample from that subject by clonal sequencing in at least 2 clones from that sample (among the subset of subjects for whom clonal sequencing is performed) if applicable.
- Emerged variant by population or deep sequencing: a post-baseline variant that is observed in 2 or more subjects of the same subgenotype by population or deep sequencing.
- Linked variant by population or deep sequencing: 2 or more signature resistance associated or emerged amino acid variants identified within a target by population or deep sequencing, and no mixture of amino acids is detected at either position.
- A linked variant by clonal sequencing will be performed: at least 2 clones from a given sample containing the same 2 or more signature resistance-associated amino acid variants by clonal sequencing, if applicable.

For all subjects, the HCV amino acid sequence as determined by population or deep sequencing at baseline will be compared to the appropriate prototypic reference amino acid sequences. A listing by subject of all baseline variants relative to prototypic reference sequence at signature resistance-associated amino acid positions will be provided for each DAA target (NS3, NS5A, and NS5B).

The following analyses will be performed on the samples from subjects who are in the PVF population and have post-baseline resistance data available.

The HCV amino acid sequence as determined by population or deep sequencing at the time of VF or the sample closest in time after VF with an HCV RNA level of ≥ 1000 IU/mL will be compared to the baseline and appropriate prototypic reference amino acid sequences. A listing by subject and time point of all post-baseline variants detected by population or deep sequencing relative to the baseline amino acid sequences will be provided across all DAA targets (NS3, NS5A, and NS5B).

The number and percentage of subjects with post-baseline variants at signature amino acid positions or emerged variants at non-signature amino acid positions by population or deep sequencing, listed by amino acid position and variant within a DAA target at the time of VF compared to baseline will be summarized, along with the number of subjects within a DAA target and overall. The analyses will be grouped by HCV subgenotype (1a or 1b) and DAA target (NS3, NS5A, or NS5B) and will list the subject numbers of subjects with each variant. The number of subjects with resistance variants in 3 targets, 2 targets or 1 target will be provided.

In addition, a listing by subject and time point of all post-baseline variants (by population or deep sequencing) at signature resistance-associated amino acid positions relative to the appropriate prototypic reference amino acid sequences will be provided.

Linkage between emerged or signature variants by population or deep sequencing will also be evaluated. A listing by subject and time point of the linked variants by population or deep sequencing for each target will be provided.

If clonal sequencing is performed, listings by subject of post-baseline variants by clonal sequencing will be provided for each DAA target. Listings of post-baseline variants by clonal sequencing by subject, amino acid position and variant within a DAA target, and time point will be provided.

For all subjects who experience VF, the persistence of resistance-associated variants for each target (NS3, NS5A, and NS5B) will be assessed by population or deep sequencing. If deep sequencing is not performed, clonal sequencing will be performed if no resistance

associated variants are detected by population sequencing at Post-Treatment Weeks 24 and 52 and at time points up to Post-Treatment Week 260 (5 years).

The number and percentage of subjects with post-baseline variants at signature amino acid positions by population or deep sequencing, listed by amino acid position and variant within a DAA target at each Post-Treatment time point compared to baseline will be summarized, along with the number of subjects within a DAA target and overall. Additionally, the number and percentage of subjects in whom a signature variant persisted at Post-Treatment Weeks 24 and 52 and time points up to Post-Treatment Week 260 (5 years) out of the total number of subjects with that emerged variant at the VF time point and at that time point will be summarized by DAA target, and variant.

The number and percentage of subjects who still have a RAV at a given Post-Treatment time point will be calculated out of all subjects with that RAV at VF who have sequencing at that time point applying the missing data imputation described in Section 6.3. If resistance-associated variants are not detected by population, clonal or deep sequencing in a given target for a subject either at the time of failure or in a post treatment sample, then that target will not be sequenced in subsequent samples from that subject.

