6.3 Missing Data Imputation

No data will be imputed for any efficacy or safety analyses except for the PRO questionnaires, for analyses of the HCV RNA endpoints, and for analysis of the persistence of resistance. If a respondent answers at least 50% of the items in a multi-item scale of the SF-36v2, the missing items will be imputed with the average score of the answered items in the same scale. In cases where the respondent did not answer at least 50% of the items, the score for that domain will be considered missing. Similarly, the missing items of the FACIT-F questionnaire will be imputed with the average score of the answered items in the same scale as long as more than 50% (≥ 7 out of 13) of the items in the scale are answered. The SF-36v2 Mental and Physical Component Summary measures will not be computed if any domain is missing.

HCV RNA values will be selected for an SVR analysis based on visit windows as defined in Section 6.2. When there is no HCV RNA value in a visit window based on defined visit windows, the closest values before and after the window, regardless of the value chosen for the subsequent and preceding window, will be used for the flanking imputation described below.

If a subject has a missing HCV RNA value at a post-Day 1 visit but with undetectable or unquantifiable HCV RNA levels at both the preceding value and succeeding value, the HCV RNA level will be considered undetectable or unquantifiable, respectively, at this visit for this subject. In addition, if a subject has an unquantifiable HCV RNA level at the preceding value and an undetectable HCV RNA level at the succeeding value, or vice versa, the HCV RNA level will be imputed as unquantifiable at this visit for this subject. For SVR analysis, if there is no value in the appropriate window after flanking imputation but there is an HCV RNA value after the window, then it will be imputed into the SVR window. Subsequent to this flanking imputation, if a subject is missing a value for the visit window associated with the analysis, the subject will be imputed as a visit failure (i.e., not undetectable or unquantifiable).

If a subject starts another treatment for HCV, then all HCV RNA values for this subject measured on or after the start date of the new HCV treatment will be excluded from analyses. The subject will be considered a failure for summaries of viral response at all time points after the start of the new HCV treatment.

HCV RNA < LLOQ Analyses for SVR

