If a subject is missing an HCV RNA value for the visit window associated with the analysis of SVR after performing the imputations described above, then this value will be imputed with an HCV RNA value from a local laboratory if present; otherwise, the HCV RNA value for this visit will be missing. Subjects with missing HCV RNA data in the analysis window, after imputations, will be imputed as a failure.

HCV RNA Analyses for Relapse and Virologic Failure

If HCV RNA values from the central laboratory are missing but a local laboratory value is present in the appropriate time period, then the local laboratory value will be used to assess post-treatment relapse and on-treatment virologic failure.

Finally, missing sequence data will be imputed as follows in the analysis of the persistence of resistance from the sequences from PT Week 52 through PT Week 260 (5 years). If a signature variant is not detectable by population, clonal or deep sequencing at PT Week 24 (or later), the variant is imputed as not detectable at the PT Week 52 (or timepoints after the sequence with the variant not detectable) and time points thereafter if a sample from Post-Treatment Week 52 or later is not sequenced. If a signature variant is detectable by population, clonal, or deep sequencing at Post-Treatment Week 52 or later, then the variant is imputed as being detectable at earlier time points if the sample at the earlier time point is not sequenced.

7.0 Demographics, Baseline Characteristics, Medical History, and Previous/Concomitant Medications

Demographics, baseline characteristics, medical history, and previous/concomitant medications will be summarized overall and by presence of cirrhosis and genotype 1 subtype on the safety population.

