Breakthrough = confirmed HCV RNA \geq LLOQ after HCV RNA < LLOQ during treatment, or confirmed increase from nadir in HCV RNA (two consecutive HCV RNA measurements > 1 log₁₀ IU/mL above nadir) at any time point during treatment. A single breakthrough value (\geq LLOQ or > 1 log₁₀ IU/mL above nadir) followed by lost to follow-up will be considered a breakthrough (i.e., will not require confirmation).

On-treatment virologic failure = breakthrough or failure to suppress during treatment (all on-treatment values of HCV RNA \geq LLOQ) with at least 6 weeks (defined as study drug duration \geq 36 days) of treatment.

RVR (rapid virologic response) = HCV RNA < LLOQ in the Week 4 window.

EOTR (end of treatment response) = HCV RNA < LLOQ in the Week 12 window for subjects receiving 12 weeks of treatment and in the Week 24 window for subjects receiving 24 weeks of treatment.

SVR₄ = HCV RNA < LLOQ in the SVR₄ window (4 weeks after the last actual dose of study drug) without any confirmed quantifiable (\geq LLOQ) post-treatment value during that SVR window.

SVR₁₂ = HCV RNA < LLOQ in the SVR₁₂ window (12 weeks after the last actual dose of study drug) without any confirmed quantifiable (\geq LLOQ) post-treatment value before or during that SVR window.

SVR₂₄ = HCV RNA < LLOQ in the SVR₂₄ window (24 weeks after the last actual dose of study drug) without any confirmed quantifiable (\geq LLOQ) post-treatment value before or during that SVR window.

Relapse₁₂ = confirmed HCV RNA \geq LLOQ between end of treatment and 12 weeks after last actual dose of active study drug (up to and including the SVR₁₂ assessment time point) for a subject with HCV RNA < LLOQ at Final Treatment Visit who completes treatment.

Relapse₂₄ = confirmed HCV RNA \geq LLOQ during SVR₂₄ window among subjects who achieved SVR₁₂ and have data available during the SVR₂₄ window.

Relapse_{late} = confirmed HCV RNA \geq LLOQ at any time after the SVR₂₄ assessment time point for a subject who achieved SVR₂₄ and has post-SVR₂₄ HCV RNA data available.

Relapse_{overall} = confirmed HCV RNA \geq LLOQ between end of treatment and up to and including the last HCV RNA measurement collected in the PT Period for a subject with HCV RNA < LLOQ at Final Treatment Visit who completes treatment. Also, include a summary of **Relapse_{overall}** for subjects who prematurely discontinued treatment (< 77 days for subjects assigned to 12 weeks of treatment and < 154 days for subjects assigned to 24 weeks of treatment).

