10.7 Additional Efficacy Analyses

The following additional HCV RNA efficacy endpoints will be summarized and analyzed on the ITT-II population, as specified:

- The number and percentage of subjects with on-treatment virologic failure;
- The number and percentage of subjects with post-treatment relapse;
- The number and percentage of subjects with RVR;
- The number and percentage of subject with EOTR;

- The number and percentage with unquantifiable HCV RNA at each post-baseline visit throughout the Treatment Period (using data from the central laboratory as observed, i.e., no imputation for missing data);
- The percentage of subjects with HCV RNA < LLOQ 24 weeks after the last actual dose of study drug (SVR₂₄);
- Reasons for not achieving SVR₂₄ for subjects who do not;
- Mean change from baseline in prothrombin time/International normalized ratio (PT/INR), FibroTest and albumin to each applicable post-baseline time point;
- The number of subjects who fail to suppress and accompanying listing;
- The number of subjects who breakthrough any time during treatment and accompanying listing;
- The number of completers with final on-treatment HCV RNA < LLOQ who relapse within the SVR₄ window, SVR₁₂ window, or SVR₂₄ window and accompanying listing;
- The concordance between SVR₁₂ and SVR₂₄ will be assessed.

In the above analyses that use the number and percentage of responders, two-sided 95% Wilson score confidence interval for a binomial proportion will be calculated.

Imputations for missing data will be performed as described in Section 6.3 for analyses of SVR, RVR, and EOTR where a missing response will be imputed as a failure after performing the described imputation. All other endpoints will be presented using data as observed. For the change from baseline to each post-baseline time point in PT/INR, Fibrotest, and albumin, descriptive statistics will be calculated.

The number and percent of subjects who fail to suppress HCV RNA and received at least 6 weeks of treatment (active study drug duration \geq 36 days) will be tabulated along with the subject numbers corresponding to the subjects who failed to suppress.

The number of subjects who breakthrough at any time during treatment and within each protocol-specified visit (defined in Table 2) will be summarized along with a corresponding listing displaying the subject numbers at the first occurrence of breakthrough.

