The number of completers (defined as study drug duration ≥ 77 days for subjects assigned to 12 weeks of treatment and ≥ 154 days for subjects assigned to 24 weeks of treatment) with final on treatment HCV RNA $< \text{LLOQ}$ who relapse within the SVR₄ window, within the SVR₁₂ window, within the SVR₂₄ window (defined in Table 3), after the SVR₂₄ window and anytime post-treatment (study drug end day ≥ 3) will be summarized along with a corresponding listing displaying the first occurrence of relapse. A similar table and listing will be provided of Preterm Relapses for subjects who do not complete treatment (defined as study drug duration < 77 days for subjects assigned to 12 weeks of treatment and < 154 days for subjects assigned to 24 weeks of treatment) with HCV RNA $< \text{LLOQ}$ at the Final Treatment visit.

The concordance between SVR₁₂ and SVR₂₄ will be assessed by agreement between SVR₁₂ and SVR₂₄ and by the positive predictive value (PPV) and the negative predictive value (NPV) of SVR₁₂ on SVR₂₄. The agreement between SVR₁₂ and SVR₂₄ is defined as the number of subjects achieving both SVR₁₂ and SVR₂₄ and the number of subjects not achieving both SVR₁₂ and SVR₂₄ out of all subjects in the ITT-II population. The PPV of SVR₁₂ on SVR₂₄ is the proportion of subjects who achieve SVR₂₄ out of all subjects who achieved SVR₁₂. The NPV of SVR₁₂ on SVR₂₄ is the proportion of subjects who do not achieve SVR₂₄ out of all subjects who do not achieve SVR₁₂.

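### SAP 10.8 and 10.7: one-directional imputation pulls reported resistance persistence down, and missing SVR24 counted as failure blurs the SVR12–SVR24 predictive values

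*SAP*

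**What the plan says.** **Persistence.** SAP Section 6.3 has two rules for missing sequence data.

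- If a variant is not detectable at Post-Treatment Week 24 or later, then "the variant is imputed as not detectable at the PT Week 52" visit and at later time points that are not sequenced.
- For a variant found by sequencing from Week 52 onward, the rule reads: "then the variant is imputed as being detectable at earlier time points if the sample at the earlier time point is not sequenced".

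No rule carries a detected variant forward. Section 10.8 computes the percentage still carrying a variant among subjects with that variant at failure "who have sequencing at that time point applying the missing data imputation described in Section 6.3". It also stops sequencing a target once no resistance-associated variants are found in it, and it sequences only samples with HCV RNA of at least 1000 IU/mL.

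**Concordance.** SAP Section 10.7 defines agreement between SVR12 and SVR24 "out of all subjects in the ITT-II population". PPV is taken over all SVR12 achievers and NPV over all non-achievers. For SVR endpoints the section applies the Section 6.3 imputation, "where a missing response will be imputed as a failure after performing the described imputation". By contrast, Relapse24 in Section 10.1 is limited to subjects who achieved SVR12 "and have data available during the" SVR24 window, and the list of reasons for SVR24 non-response gives missing follow-up its own category.

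**The concern.** In the persistence table the two kinds of subject are treated differently. A subject who lost the variant remains at every later visit by imputation. A subject last seen with the variant, and not sequenced again, disappears from both numerator and denominator. Carriers can leave by dropping out or because HCV RNA falls below the sequencing threshold, for example after successful retreatment. The table could then show resistance fading over five years when part of the decline comes from a changing denominator.

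In the concordance analysis, PPV is meant to show how often an SVR12 response is still present at Week 24. With missing SVR24 scored as failure, PPV mixes relapse with loss to follow-up. NPV errs the other way: a subject missing both windows is scored as a correct prediction.

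**Working it through.** The documents state no figure for persistence, PPV or NPV, so there is none to reproduce.

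**Inputs from the documents.** 600 planned subjects, 4% without SVR12, and dropout of up to 20% (SAP Section 4.3). This gives 600 × 0.04 = 24 non-responders and 576 responders. Reading the 20% as five-year dropout is an assumption. Rates of variant loss, exit from sequencing, and relapse after Week 12 are not given and are assumed below.

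**Persistence: direction.** Let S(t) be true persistence and G(t) the share still sequenced, with exit unrelated to variant status. The SAP percentage at visit t is

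S(t)G(t) / [S(t)G(t) + Σ (S(v−1) − S(v))G(v)], summed over visits v up to t.

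G never rises, so the sum is at least G(t)(1 − S(t)). The denominator is then at least G(t), and the percentage cannot exceed S(t).

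**Count example (assumed).** Of 20 carriers at failure, 4 lose the variant by Week 52 and none later. Week 52 shows 16/20 = 80%. If 8 of the 16 remaining carriers are not sequenced at Week 260, the SAP rule gives 8/(8 + 4) = 66.7%, while Kaplan-Meier stays at 16/20 = 80%. The reported figure falls with no further loss. With no loss at all and the same 8 leaving, it is 12/12 = 100%.

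**Size at Week 260, constant rates of variant loss and exit.** Visits are at Weeks 24, 52, 104, 156, 208 and 260.

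| True persistence | 80% still sequenced | 50% | 30% |
|---|---|---|---|
| 90% | 89.1% | 86.8% | 83.6% |
| 70% | 67.8% | 62.7% | 56.3% |
| 50% | 47.3% | 41.4% | 34.8% |
| 30% | 27.6% | 22.8% | 17.9% |

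A simulation of 24 carriers (20,000 runs) gave 47.3%, 41.5% and 34.8% for a true 50%, and 83.8% for a true 90% with 30% still sequenced.

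**Early loss makes it larger.** Suppose 30% of variants are lost by Week 24 and none later, so true persistence is 70%.

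- 80% of carriers still sequenced at Week 260: (0.70 × 0.80) / (0.70 × 0.80 + 0.30) = 0.56/0.86 = 65%.
- 30% still sequenced: 0.21/(0.21 + 0.30) = 41%.

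Adding 10% variant loss per year gives true persistence of 0.70 × 0.9⁵ = 41%, against about 37% under the SAP rule when 20% leave over five years.

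**PPV.** Under the SAP rule PPV = (1 − loss)(1 − relapse); among subjects with SVR24 data it is 1 − relapse. Dropout of 20% spread evenly over 260 weeks gives a 12-week loss of 1 − 0.8^(12/260) = 1.02%, or 576 × 0.0102 ≈ 5.9 responders.

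- No relapse: PPV = 99.0% under the rule, 100% in observed data.
- Assumed relapse of 0.2% (about 1.1 subjects): 98.8% against 99.8%.
- The same relapse with assumed loss of 2% or 5%: 97.8% or 94.8% against 99.8%.

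**NPV.** A subject whose SVR12 is missing after imputation has no later HCV RNA value, since one would have been back-filled. SVR24 is then also a failure, and the pair counts as a correct prediction. As an assumed example, take 24 non-responders, 8 of them missing both windows, and 1 of the other 16 reaching SVR24. NPV is 23/24 = 95.8% by the rule and 15/16 = 93.8% in subjects with data. If none of the 16 reaches SVR24, both are 100%, but 8 of the 24 apparent confirmations carry no information.

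**The case against.** Much of the case on the other side stands.

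- **Carrying non-detection forward is needed in a by-visit table.** Sequencing of a target stops once its variants are gone. Without the rule, confirmed losses would vanish and persistence would be biased upward. Only the lack of any matching treatment for carriers is at fault.
- **Backward imputation limits the problem.** A carrier who misses a visit and is later found positive is restored.
- **The cells are small.** The 24 planned non-responders include missing data and early discontinuation, and results are split by target and variant. Even with 24 carriers, the standard error at 50% is √(0.25/24) ≈ 10 points, larger than the bias at 20% exit. The SAP also reports counts, and Protocol Section 8.1.3 promises listings in a subset of subjects.
- **The concordance effect is limited.** Flanking, back-fill and local-laboratory values are applied first, and missing = failure is the SAP's usual SVR convention.

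Some stronger readings are tempting but not supported. A reader might infer that persistence falls even when no variant is ever lost; the count example shows it stays at 100%. Assuming 30% of carriers leave each year would give 28% at year 5 against a true 70%, but that rate removes 83% of carriers (1 − 0.7⁵) and no document supports it. A reader might also infer that the SAP classes lost subjects as relapses. It does not: Relapse24 and the SVR24 reasons table keep missing data apart, and the blurring is confined to the concordance measures. Nor does either document say that concordance is used to validate SVR12; SAP Section 10.7 lists it among additional analyses.

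**Conclusion.** Both rules distort the summaries they feed, and neither distortion is a matter of chance. For persistence the direction is downward, provided exit from sequencing is unrelated to variant status and some variants have already been lost. The size rests on rates the documents do not give: about 1–5 points at Week 260 if 20% of carriers leave over five years, and about 6–15 points or more if 70% or more leave, the larger values arising when variants are lost early. Retreatment of virologic failures could push exit above the planning dropout, but by how much is unknown.

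For concordance, evenly spread 20% dropout costs PPV about one point. Those roughly 6 lost responders would outnumber the relapses at the low rates assumed (about 1 at 0.2%), so most of the shortfall from 100% could be loss to follow-up. NPV and agreement are inflated by subjects missing both windows.

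These are descriptive, non-primary summaries. The clinical-outcome analysis and the SVR12 endpoint are not affected. The change is still worth making, because a denominator artefact in the persistence table could be read as reversion.

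**What to change.** **SAP Section 10.8.** Estimate persistence as time from virologic failure to first non-detection, by Kaplan-Meier or an interval-censored method given the wide visit spacing, censoring carriers at their last sequenced sample. If a by-visit table is kept, show the number observed and the number imputed at each visit.

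**SAP Section 10.7.** Compute agreement, PPV and NPV among subjects with both SVR12 and SVR24 data (observed, flanked or back-filled), and state how many are excluded. Keep the missing = failure version as a supplement if wanted.

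The cost is SAP wording and reprogramming of two summaries. No new data are needed.
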